## **7.0 Study Withdrawal/Discontinuation**

A participant may withdraw from the study at any time verbally or by providing this request in writing as described in the informed consent document. As outlined in the consent document, if the participant/patient wishes to withdraw consent, the PI will:

- no longer use and take reasonable steps to destroy all saliva samples and information
- not take back any research / analyses already completed

## **8.0 Statistical Considerations**

Non-PHI primary data will be stored electronically on both the measurement instruments and as Excel and/or Prism data files on the PI's university-supplied, DUO-protected laptop computer. The laptop is backed up automatically by UITS, whereas the instrument data files will be backed up manually on a monthly basis. Other data sources include the subjects' sex, age, and body mass will be collected as paper records and merged with the primary data as needed. Data quality will be assured by random auditing of single entry results and extraction/examination of data used for subsequent statistical analysis every 6 months.

Statistical analyses will be performed using Prism® version 8.0.1 (GraphPad Software, La Jolla, CA). Normality of data distribution will first be tested using the D'Agostino-Pearson omnibus test. Analysis of individual endpoints will then be conducted using a mixed model analysis of variance (ANOVA) approach, with treatment and trial number as fixed effects and subject as a random effect to account for repeated measurements. Post-hoc testing will be performed using the Šidák-Holms multiple comparison approach. A P value of <0.05 will be considered significant.

As this is a pilot experiment, we lack the preliminary data necessary to perform a formal sample size/power analysis. In previous research, however, we have observed than an *increase* in NO bioavailability resulting from ingestion of NO3-rich beet juice *increased* ( $P<0.05$ ) Vmax and Pmax by  $11.4\pm16.5$  and  $6.3\pm8.7\%$ , respectively. Assuming similar intersubject variability when NO bioavailability is *reduced* by use of an antibacterial mouthwash, our chosen sample size will allow us to detect any effect size  $\geq1.3$  with an alpha of 0.05 and 1-beta of 0.80.

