## 2.0 Rationale and Specific Aims

**Specific Aim #1:** To determine the effects of antibacterial mouthwash on maximal knee extensor speed and power in healthy young men and women.

We hypothesize that use of an antibacterial mouthwash will significantly reduce maximal knee extensor speed and power (primary endpoints). This will be accompanied by significant reductions in salivary  $\text{NO}_3^-/\text{NO}_2^-$  and breath NO levels (secondary endpoints).

We will test these hypotheses using isokinetic dynamometry and salivary and breath sampling in **n = 24** healthy young men and women (n = 8/group).

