### **4.0 Enrollment/Randomization**

Study participants will be given a consent form ahead of the screening visit. The study participant will be given time to review the consent form, and a study staff member will contact the potential subject to answer any questions they may have. If interested, then the potential subject will be scheduled for a meeting where the consent form will be reviewed again. The potential subject will be given as much time

as they wish to consider participation before signing the consent form and if they wish to move forward with participating, then the consent form will be signed by both the study participant and the person who reviewed the consent and obtained the participant's signature. A copy of the signed consent form will be provided to the subject. Both the participants and the investigators will be blinded to the order of treatment, which will be randomized in four blocks of four using randomization.com.

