## 5.0 Study Procedures

### Study Design

**Figure 1. Overall study design.**

### Study Procedures

**Study Visit 1** (Screening and muscle function testing practice): The consent statement will be reviewed with the subject including the procedures of the study and the risks of participating. Subjects will also be instructed on the requirements while in the study including not exercising on the day of study visits prior to the visit and to not attend the visit in a fasting or hungry state. They will also be asked to not consume caffeine or alcohol or use chewing gum in the 24 hours prior to the visit. They will be asked to avoid consuming foods (e.g., spinach, beets, collard greens) high in  $\text{NO}_3^-$  during this 24 hour period and to not use any other mouthwash products other than those provided during the study. Subjects who decide to participate will sign the consent and complete a screening to determine if they are eligible. If they are determined to be eligible they will then be asked to practice the muscle function test that will be used during the study that assesses the contractile function, i.e., maximal knee extensor speed and power, of the knee extensors of the subject's dominant leg. This is done using a Biodex 4 Isokinetic Dynamometer (Biodex Medical Systems, Shirley, NY).

**Study Visit 2** (Baseline Testing): participants will be asked to return and undergo baseline testing. This will include 1) collection of a saliva sample for a measurement of  $\text{NO}_3^-$  and  $\text{NO}_2^-$ , and, 2) assessment of the muscle function of the knee extensors (see Study Methods). The subjects will then be randomly assigned (via randomization.com) in four blocks of four subjects each to receive either an antibacterial mouthwash (Cepacol®, Reckitt Benckiser, Parsippany, NJ) or, as a control solution, an alcohol-free "natural" mouthwash (Tom's of Maine®, Kennebunk, ME). Participants will be asked to rinse their mouth as directed on the product's packaging for 30 s twice per day for 7 days and to record the usage of the mouthwash on a provided form. Subjects will then return for Study Visit 3. Note that although the two products differ significantly in terms of packaging, color, taste, etc., the subjects will be told that the study is simply to compare the two products, with no expectation as to the outcome.

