**Study Visit 3** (Final Testing), participants will be asked to return to undergo the same procedures as described above for Study Day 2.

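### Section 8.0 does not say which test decides the hypothesis; the treatment term it lists, if coded as assigned product at both visits and used as that test, estimates half the effect

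*Combined protocol and SAP*

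**What the plan says.** Section 2.0 hypothesizes that "use of an antibacterial mouthwash will significantly reduce maximal knee extensor speed and power (primary endpoints"), so there are two primary endpoints, Vmax and Pmax, and the expected direction is a decrease.

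Section 5.0 has muscle function measured at Visit 2, before assignment. Then: "The subjects will then be randomly assigned (via randomization.com) in four blocks of four subjects each to receive either an antibacterial mouthwash" or a control mouthwash. Each subject uses one product for 7 days, and at Visit 3 "participants will be asked to return to undergo the same procedures as described above for Study Day 2". No second treatment period is described. Section 4.0, however, says: "Both the participants and the investigators will be blinded to the order of treatment".

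Section 8.0 gives the model for each endpoint, "with treatment and trial number as fixed effects and subject as a random effect to account for repeated measurements", followed by Šidák-Holms post-hoc testing. The decision rule is "A P value of <0.05 will be considered significant". The section does not name an interaction, a change score, a baseline covariate or a primary contrast. It also does not give the coding of treatment at Visit 2, the sidedness, or the list of post-hoc comparisons. The sizing statement is a detectable effect of at least 1.3 "with an alpha of 0.05 and 1-beta of 0.80".

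**The concern.** In a design with one pre-assignment and one post-assignment measurement, the product effect appears only at the second visit. The comparison that answers section 2.0 is therefore the between-arm difference in change, or the Visit 3 difference adjusted for Visit 2. The two fixed effects listed in section 8.0 do not by themselves provide it. A main effect of assigned product includes the Visit 2 measurements, taken before any product was used, and so dilutes the effect.

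Two things are at stake. First, one natural reading of the listed terms targets half the effect and, when the visits are positively correlated, has less power than the comparison of changes. Second, several tests of the same hypothesis remain open and can give different P values, so the choice could be made after the data are seen. With 8 to 12 subjects per arm, that choice could decide the result.

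**Working it through.** **Inputs from the documents.** Alpha 0.05, power 0.80 and effect size 1.3 (section 8.0). The ± values for percentage change in the cited beet juice study are 16.5 for Vmax and 8.7 for Pmax (section 8.0). Group size is 8 per arm, from "healthy young men and women (n = 8/group") and from four blocks of four over two products (16/2 = 8). The alternative is 12 per arm, from a total of 24 over two products.

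**Assumptions not in the documents.** The Visit 2 to Visit 3 correlation ρ; sidedness (both shown); ± read as an SD; 1.3 read in SDs of change; equal variance at the two visits; complete data.

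**1. The plan's own figure.** For a two-sample t-test with 8 per group (14 df, noncentral t), the effect detectable with 80% power is 1.308 one-sided and 1.507 two-sided. The stated 1.3 is therefore reproduced one-sided (power 79.6%) and not two-sided (67.7%).

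**2. What each term estimates.** Let the true effect δ be present only in the antibacterial arm at Visit 3.

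- Assigned-product main effect: (0 + δ)/2 = 0.5δ.
- Treatment-by-trial interaction: δ − 0 = δ.
- Treatment coded as product in use at each visit: δ.
- Between-product comparison at Visit 3: δ.

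Generalized least squares on the expected cell means gives exactly 0.50δ for the additive assigned-product model, and δ for the exposure-coded model, at ρ = 0.5, 0.8 and 0.9. Simulated ratios for the main effect (20,000 trials per setting) are 0.500, 0.501 and 0.498.

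Under the assumptions above, 1.3 SD of change is 1.3 × 16.5 = 21.5% for Vmax and 1.3 × 8.7 = 11.3% for Pmax. The main effect would estimate 10.7% and 5.7%.

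**3. Power.** Set the raw SD to 1, so the SD of change is √(2(1−ρ)) and δ = 1.3√(2(1−ρ)). With n per arm and 2n − 2 df:

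- Interaction: ncp = 1.3/√(2/n). For n = 8 this is 2.60.
- Main effect: ncp = (δ/2)/√((2/n)(1+ρ)/2), which equals the interaction ncp × √((1−ρ)/(1+ρ)). For n = 8 and ρ = 0.5 this is 2.60 × 0.577 = 1.50.

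Main-effect power by ρ, with interaction power in the last column:

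| n per arm, sides | ρ = 0 | 0.3 | 0.5 | 0.7 | 0.9 | Interaction |
|---|---|---|---|---|---|---|
| 8, two-sided | 68% | 43% | 29% | 17% | 9% | 68% |
| 8, one-sided | 80% | 57% | 41% | 27% | 14% | 80% |
| 12, two-sided | 86% | 61% | 42% | 25% | 11% | 86% |
| 12, one-sided | 92.5% | 73% | 55% | 36% | 17% | 92.5% |

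Simulation (40,000 trials per setting) agrees. The effect that the main effect could detect with 80% power, 8 per arm, one-sided, is 1.308 × √((1+ρ)/(1−ρ)) = 2.27, 3.11 and 5.70 SD of change at ρ = 0.5, 0.7 and 0.9.

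**4. Sensitivity to the scale of 1.3.** Holding 1.3 in SDs of change shrinks the raw effect as ρ rises, which accounts for part of the fall to 9%. If 1.3 is read in raw SDs instead (8 per arm, two-sided), main-effect power is 29%, 26% and 24% at ρ = 0.5, 0.7 and 0.9. Interaction power is then 68%, 88% and 100%, so the gap does not close.

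**5. Adjusting for Visit 2.** Simulated ANCOVA power, 8 per arm, two-sided, is 76%, 71% and 67% at ρ = 0.5, 0.7 and 0.9, against 68% for the interaction. The gain is about 8 points, then about 4, then none (slightly negative).

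**The case against.** The half-effect result needs two things the plan does not state: that treatment means assigned product at both visits, and that its main effect decides. A list of fixed effects does not exclude an interaction. The planned Šidák-Holms step even counts against the main-effect reading. With two products and two visits, each factor has two levels, so a multiple-comparison procedure has work to do only if product-by-visit cell means are compared. A between-product comparison at Visit 3 would target the full effect. All of this stands, and it makes the half-effect scenario one possibility, not a prediction. It does not close the gap: the comparisons are not listed, and no test is named as decisive.

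The reference in section 4.0 to an order of treatment suits a crossover, where treatment plus trial number with random subject would estimate the full effect. Section 5.0 gives each subject one product and one treatment period, so the crossover reading does not fit the schedule. The two sections need to be reconciled.

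A reader might infer from the stated 1.3 that the sponsor sized the trial on a comparison of changes. The documents do not support that. The value 1.31 comes from any one-sided two-group comparison with 8 per group, whatever the outcome. Three groups of 8 (24/8, with 21 df) give 1.29 one-sided, which also rounds to 1.3, although section 5.0 names only two products.

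The correlation is not given, so the power losses are a range that starts at zero. Section 8.0 also calls the study a pilot without a formal power analysis. That tempers the importance, but section 2.0 still names primary endpoints and section 8.0 still sets a significance threshold.

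**Conclusion.** The point holds in conditional form and should be fixed. That section 8.0 names no deciding test, interaction or baseline adjustment is a plain reading of the text and needs no assumption. The factor of one half is exact for assigned-product coding with two equally weighted visits, complete data and arms equal at baseline in expectation; it does not depend on the correlation.

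The power loss does depend on it. Using the table's 8-per-arm, two-sided row, the loss relative to the interaction is nil at ρ = 0, 25 points at 0.3 (68 − 43), and 39, 51 and 59 points at 0.5, 0.7 and 0.9. These figures also rest on reading 1.3 in SDs of change.

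A reader might conclude that the planned analysis will halve the effect. The documents do not support that: they leave open exposure coding, an interaction and Visit 3 cell comparisons, each of which targets the full effect.

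**What to change.** In section 8.0, name one primary test for each of Vmax and Pmax:

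- preferably, the between-arm difference at Visit 3 adjusted for the Visit 2 value (ANCOVA, or an equivalent mixed model with a common Visit 2 mean);
- at minimum, the treatment-by-trial interaction, i.e. the between-arm difference in change.

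Report it with a 95% CI. State how treatment is coded at Visit 2, the sidedness (so that it agrees with the stated 1.3 at 80% power), and which post-hoc comparisons are planned. Say that the conclusion will not rest on the treatment main effect or on within-arm tests. Reconcile the order-of-treatment phrase in section 4.0 with the one-product-per-subject schedule in section 5.0.

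The cost is one paragraph in section 8.0 and one phrase in section 4.0. No new data are needed, because the Visit 2 value is already collected. The interaction costs nothing; ANCOVA costs one degree of freedom (13 instead of 14 with 8 per arm, 21 instead of 22 with 12). Most of the benefit comes from naming a test that targets the full effect; ANCOVA is a smaller addition.

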## **9.0 Privacy/Confidentiality Issues**

All study activities will be performed within areas respective of the participants' right to privacy.

Although there can be no absolute guarantee of confidentiality, every practical precaution will be taken.

Each study participant will be assigned a unique ID. Samples and information will be de-identified using this unique ID.

## **10.0 Follow-up and Record Retention**

Study recruitment will be ongoing. The duration of the entire study is expected to be about 8 mo.

Any remaining saliva samples will be de-identified and discarded. The de-identified data will be retained on computer files indefinitely. Hard copy study documents will be kept in a locked, file cabinet in a locked room. De-identified electronic study information will be stored on a specified password-protected network that is backed up daily. Only the study team and the relevant personnel will have access. Files will be kept on site until 2 y after study completion, and then sent to a secure archiving facility. Files will be kept as long as required by law.

